#### 4.2.2.2.5 Duration

Duration is derived from the start and end dates of the unsolicited AE:

- Duration = End date of unsolicited AE - start date of unsolicited AE + 1

The duration is considered as missing only if one or both start and end dates of the unsolicited AE is missing or partially missing.

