#### **8.3.3 Follow-up of AEs and SAEs**

After the initial AE/SAE report, the investigator is required to proactively follow each participant at subsequent visits/contacts, unless a participant refuses further contact. All AEs that are

considered by the investigator as serious, or related to the study intervention administered, or that led to study or vaccination discontinuation, or AESIs (as defined in [Section 8.3.6](#)), will be followed during the conduct of the study until resolution, stabilization, or the participant is lost to follow-up (as defined in [Section 7.3](#)). For related SAEs ongoing at last study visit, such follow-up may need to continue after the end of the study.

Further information on follow-up procedures is provided in [Appendix 10.3](#).

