### 3.4.3 Secondary Endpoints

#### Safety

For the main safety parameters, 95% CIs of point estimates will be calculated using exact binomial method (Clopper-Pearson method) for single proportions and using the normal approximation for quantitative data.

All analyses will be descriptive; no hypotheses will be tested.

The number of participants with documented safety will be used as denominator of the frequencies:

- For solicited reactions, the denominator will be the total number of participants who have non-missing data for the endpoint considered.
- For unsolicited AEs, the denominator will be the total number of participants who were vaccinated with the dose analyzed.

In terms of contents, solicited reactions will be presented by time to onset, maximum severity, number of days of occurrence and action taken; unsolicited AEs will be presented by causal relationship, time of onset, maximum severity, and duration; SAEs will be presented by causal relationship, seriousness, and outcome.

Subgroup analysis will also be performed; in particular, the main safety endpoints will be summarized according to age subgroups, sex, and race, as appropriate according to number of participants in the respective subgroups.

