##### **3.4.4.2.4 Start Date and End Date**

Missing or partially missing start dates or end dates for unsolicited AEs (including SAEs) will remain missing and not be imputed. If the start date is missing or partially missing, the time of onset will be set to missing. If either the start date or end date is missing or partially missing, the duration will be considered missing.

Missing or partially missing end dates for ongoing solicited AEs will remain missing and not be imputed.

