#### **4.2.2.1.6 Overall Number of Days of Occurrence**

If a reaction is ongoing at the end of the solicited period, then the overall number of days of presence is derived from the daily intensities and the end date of the reaction after the end of the solicited period. The overall number of days of presence is:

- $(\text{End date} - \text{last vaccination date}) + (\text{number of days of presence within the solicited period}) - \text{length of the solicited period} + 1$

If the end date is missing or incomplete (contains missing data), the overall number of days of presence will be considered as Missing.

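### Unsolicited adverse events still ongoing at a data cut are given a missing duration, so the planned duration summary leaves out the longest events and is biased short, mainly for Dose 2 at the D43 analysis

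*SAP*

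**What the plan says.** For unsolicited adverse events (AEs), SAP 4.2.2.2.5 computes duration as end date minus start date plus 1, and adds: "The duration is considered as missing only if one or both start and end dates of the unsolicited AE is missing or partially missing". SAP 3.4.4.2.4 states the same rule ("If either the start date or end date is missing or partially missing, the duration will be considered missing") and excludes imputation: "Missing or partially missing start dates or end dates for unsolicited AEs (including SAEs) will remain missing and not be imputed". Duration is a planned presentation. SAP 3.4.3 states that "unsolicited AEs will be presented by causal relationship, time of onset, maximum severity, and duration".

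For solicited reactions, SAP 3.4.4.2.4 says "Missing or partially missing end dates for ongoing solicited AEs will remain missing and not be imputed", and SAP 4.2.2.1.6 says "If the end date is missing or incomplete (contains missing data), the overall number of days of presence will be considered as Missing". Two neighbouring rules do not depend on an end date. SAP 4.2.2.1.5 counts days within the solicited period from the daily intensities, and SAP 4.2.2.1.7 derives an ongoing status with its own denominator in the safety tables.

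On follow-up, Protocol 8.3.3 provides that AEs that are serious, related, AESIs or the cause of discontinuation "will be followed during the conduct of the study until resolution, stabilization, or the participant is lost to follow-up". The schedules of activities in both documents collect unsolicited AEs at Visits 1 to 3 only. SAP 3.5 places the main analysis, which will help select the formulation, on data up to 21 days after the last vaccination.

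**The concern.** An ongoing event is a right-censored observation: its duration is known to be at least the time from onset to the last contact. The SAP handles it as missing data. The chance that an event is still open at the cut rises with its length, so this rule removes long events selectively. What remains is a summary of events short enough to have finished.

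The SAP makes the distinction for solicited reactions, through the ongoing status in 4.2.2.1.7, but has no ongoing category or censoring rule for unsolicited AEs. At stake is one descriptive safety summary, read at the analysis that informs the choice of formulation. A reader of that table would see durations shorter than those that occurred, and could not tell an event known to be continuing from one whose date was lost.

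**Working it through.** The documents state no figure on AE duration, so there is nothing to reproduce. The check has two parts: following the rule through the schedule, and illustrating its size under stated assumptions.

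**Following the rule.** Count the day of Dose 2 as D01, as SAP 4.2.2.2.4 does.
- Unsolicited AEs are analysed with onset from D01 to D22 after the dose.
- Visit 3 is 21 days after Visit 2 with a window of +7 days, so it falls on D22 to D29 after Dose 2.
- If no end date is recorded after Visit 3, an event with onset on day s has a duration only if it lasts at most (Visit 3 day − s + 1) days.
- For onset on D22 this is 22 − 22 + 1 = 1 day to 29 − 22 + 1 = 8 days. For onset on D01 it is 22 to 29 days.

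Late-onset events are thus cut off hardest. Dose 1 events have about three more weeks before the same cut.

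**Size at the D43 analysis, Dose 2 events.** Assumptions, none of them from the documents: onset uniform on D01 to D22; Visit 3 uniform on D22 to D29; lognormal durations with log-SD 1, rounded up to whole days; no end date recorded after Visit 3. There were 2,000,000 simulated events per row.

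| Underlying median (days) | Durations missing | Mean: all events → reported | Share lasting ≥ 15 days: all events → reported |
|---|---|---|---|
| 1.5 | 3.6% | 3.0 → 2.7 | 1.3% → 0.4% |
| 3 | 10% | 5.4 → 4.2 | 6.2% → 1.8% |
| 7 | 29% | 12.1 → 6.7 | 24% → 7.0% |
| 14 | 51% | 23.6 → 8.9 | 50% → 15% |

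With a 1.5-day median the whole-day median is 2 both for all events and as reported. With a 7- or 14-day median the reported whole-day median is 5 or 8. With a 3-day median, rounding up puts the whole-day median on the border between 3 and 4, so a one-day difference there means nothing. Onset timing also matters: with a 3-day median and all onsets on D01 to D04, only 2% of durations are missing.

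**Other distributions and cuts.** A second simulation used a fixed cut 21 days after Dose 2, with exponential and lognormal durations.
- Dose 2, D43 cut: for true means of about 3.5, 7.5 and 14.5 days, the mean of the non-missing durations was 13–18%, 34–37% and 54–57% too low.
- Dose 1, same cut: 0–3%, 5–13% and 25–30% too low.
- Dose 2, final cut, if end dates are collected to about 365 days after Dose 2: 0–2% too low, even with a true mean of about 30.5 days.

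**Solicited reactions.** Collection ends 7 days after the dose and the next visit is at least 21 days after it. That leaves at least 21 − 7 = 14 days in which to obtain an end date. Days within the period and ongoing status are kept in any case. Only the overall number of days in SAP 4.2.2.1.6 shares the gap.

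**The case against.** The strongest reply is that little of importance is lost.

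- **Vaccine reactions are mostly protected.** Solicited reactions and all injection-site events are related by convention (Protocol 10.3.3), and Protocol 8.3.3 follows related events to resolution, stabilization or loss to follow-up. The events with no such rule are non-serious, unrelated systemic AEs that are not AESIs and did not cause discontinuation. This stands. A reader might infer that the plan understates how long vaccine reactions last; the documents do not support that as a general statement.
- **Outcome may reveal ongoing events.** SAP 4.2.3.4 summarizes outcome as collected and does not confine it to SAEs, although SAP 3.4.3 names outcome only for SAEs. It would therefore be wrong to say that ongoing unsolicited AEs are shown nowhere. An outcome table would still leave the duration summary uncorrected.
- **The table layout is not visible.** The SAP is to be used with separate table shells. Time of onset has a missing category (SAP 4.2.2.2.4), and duration may have one too. That would show how many events are affected, but would mix ongoing events with unknown dates.
- **The size is assumed.** The protocol's risk table says that most injection-site and systemic reactions cleared within one or two days without treatment. Durations of that order give the small effect in the first row of the table. End dates may also arrive between Visit 3 and the lock, so losing every event open at Visit 3 is a worst case.
- **It is descriptive.** No stated criterion for choosing the formulation names AE duration. That limits the consequence, but a descriptive estimate can still be biased.

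A reader might also infer that the rule hides a difference between groups. If one group's underlying median were 7 days and another's 14, the difference in means would shrink from 23.6 − 12.1 = 11.5 days to 8.9 − 6.7 = 2.2 days. But nothing in the documents indicates that the groups differ in AE duration, so this is only a possibility.

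**Conclusion.** The point holds for the duration of unsolicited AEs. As written, the plan codes an event known to be ongoing as missing, and the summary is biased short whenever any event is open at the cut. That direction follows from the rule alone.

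The size cannot be read from the documents. At the D43 analysis it ranges from about 4% of Dose 2 durations missing with an unchanged median, if events typically last 1.5 days, to about half missing, if they typically last 14 days. These figures rest on the assumed onset pattern, the assumed lognormal shape, and no end dates being added after Visit 3. At the final lock the bias is small where end dates have been obtained. It can persist for non-serious, unrelated AEs that Protocol 8.3.3 does not require to be followed to resolution, and for events closed as stabilized or lost to follow-up.

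For solicited reactions only the overall number of days is affected. No alpha, power or sample size changes. The rule is nonetheless worth correcting before the first lock, because the correction is specific and cheap.

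**What to change.** Amend SAP 3.4.4.2.4 and 4.2.2.2.5, and 4.2.2.1.6 for the overall number of days:

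- Where an event is recorded as ongoing or not recovered at the cut, do not code its duration as missing.
- At each database lock, report the number of such events by group in a separate ongoing category beside the duration summary. Give each a minimum duration = last contact or cut-off date − start date + 1.
- Keep the missing code for unknown start dates and for resolved events with an unknown end date.
- If a median is shown, a Kaplan-Meier estimate with ongoing events censored is an option, not a necessity.

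The cost is SAP wording, one derived flag and a little programming, provided that the CRF outcome field records ongoing status. Reported durations will become somewhat longer.

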#### 4.2.2.2.6 Serious Adverse Events

An event will be considered as a serious event if “Yes” is checked for “Serious?” in the eCRF. SAEs will be analyzed within 21 days after each vaccination, from D22 to 387 days after each vaccination, and within 387 days after each vaccination.

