***Unsolicited AE/AR:***

An unsolicited AE is an observed AE that does not fulfill the conditions of solicited reactions, ie, pre-listed in the CRF in terms of diagnosis and onset window post-vaccination. For example, varicella or a solicited term such as headache starting after the solicited observation period (eg, headache starting on Day 10 post-vaccination in the case where headache occurring between the day of vaccination and the next 7 days is pre-listed in the protocol and CRF as a solicited reaction).

An unsolicited AR is an unsolicited AE that is considered related to an IMP.

Unsolicited AEs includes both serious (SAEs) and non-serious unsolicited AEs.

All unsolicited AEs occurring at and around the IMP injection/administration site are to be considered by default as related to the IMP administered at that site and are therefore referred as unsolicited injection/administration site ARs.

All unsolicited AEs which are not at and around the IMP injection/administration site, are referred as systemic unsolicited AE. For each unsolicited systemic AE, the investigator assesses the relationship to the IMP. Systemic AEs assessed as related to IMP are referred as systemic ARs.

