##### 4.2.2.2.3 Last Vaccination

Last vaccination before an unsolicited AE will be derived from the pre-visit numbers provided in the clinical database and will be calculated as follows:

- If an unsolicited AE has a non-missing pre-visit number, the pre-visit number will be used to determine the last vaccination before the unsolicited AE.

- If the pre-visit number is missing and the start date is complete (i.e., including the day), then the start date will be used to determine the last vaccination before the unsolicited AE.
- If an unsolicited AE has a missing pre-visit number and a partial start date (at least the day missing), the unsolicited AE will be considered as post injection 1.

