#### 4.2.2.2.4 Time of Onset

Time of onset is derived from the start date of the unsolicited AE and the date of vaccination:

Time of Onset = start date of the unsolicited AE - date of vaccination + 1 (if D01 is the first vaccination day).

The time of onset is considered as missing only if one or both dates are missing or partially missing.

The unsolicited AEs will be analyzed “Within 21 days” after each vaccination, which corresponds to AEs with a time of onset between D01 and D22 or missing. An AE with missing time of onset will be considered to have occurred just after the vaccination, so will be included in these tables.

Time of onset period is displayed as D01-D04, D05-D08, D09-D15, D16 or later, and missing.

**Note:** Unsolicited AE that occurred before vaccination (negative time of onset) or with a time of onset higher than defined above will not be included in analysis but will be listed separately.

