#### 4.2.2.2.7 Adverse Events of Special Interest

An event will be considered as an AESI if “Yes” is checked for “Is the event an AESI?” in the eCRF.

AESIs will be analyzed within 21 days after each vaccination, from D22 to 387 days after each vaccination, and within 387 days after each vaccination.

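### The late SAE and AESI window starts on D22, a day the early window already contains, and the 387-day limit is a study day applied to each dose

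*SAP*

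**What the plan says.** SAP 4.2.2.2.6 sets three reporting windows for serious events: within 21 days of each vaccination, "from D22 to 387 days after each vaccination, and within 387 days after each vaccination". SAP 4.2.2.2.7 repeats the three windows for events of special interest: "AESIs will be analyzed within 21 days after each vaccination, from D22 to 387 days after each vaccination, and within 387 days after each vaccination".

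The day numbering comes from SAP 4.2.2.2.4: "Time of Onset = start date of the unsolicited AE - date of vaccination + 1". The vaccination day is therefore D01. The same section defines the 21-day window as one "which corresponds to AEs with a time of onset between D01 and D22 or missing".

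SAP 4.2.2.2.3 attaches each unsolicited event to one dose. Where a pre-visit number exists, "the pre-visit number will be used to determine the last vaccination before the unsolicited AE". Without it, a complete start date is used. With neither, "the unsolicited AE will be considered as post injection 1". Protocol 10.3.1 brings SAEs under these rules: "Unsolicited AEs includes both serious (SAEs) and non-serious unsolicited AEs". Protocol 8.3.6 has AESIs captured as SAEs.

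The schedule of activities, the same in both documents, places dose 2 at D22 (+7 days) and the last visit 12 months after that visit, at D387 (+14 days).

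**The concern.** Two rows that are meant to split follow-up into an early and a late part share a day. Time since vaccination is the main way a reader judges whether a serious event could plausibly be linked to a dose, so an event should sit on one side of that boundary. As written, a programmer who follows the text enters a D22 onset twice. One who notices the overlap has to choose a side, and the SAP gives no rule for the choice.

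The upper limit has a separate problem. A day number that has meaning only when counted from dose 1 is used as a length of time after either dose. For dose 2 the row label then describes a longer period than the design follows.

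Finally, the two window sections do not say that the last-vaccination rule governs these tables, although it sits a few paragraphs earlier in the same SAP section.

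**Working it through.** **Inputs**
- Onset day = start date − vaccination date + 1 (SAP 4.2.2.2.4).
- Early window: onset D01 to D22 (SAP 4.2.2.2.4). Late window: from D22 (SAP 4.2.2.2.6 and 4.2.2.2.7).
- Dose 1 on study day 1; dose 2 on study day 22, at latest day 29 (schedule of activities, +7 days).
- Last visit 12 months after dose 2, +14 days (schedule of activities). The 12-month contact is at least 365 days after the last vaccination (Protocol 8.3.2).

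**Reproducing 387.** 1 + 21 = 22 for dose 2, and 22 + 365 = 387 for the last visit. This matches the schedule exactly and shows that 387 is counted from dose 1.

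**The shared day.** Taking the late window as D22 to D387:
- Early window: 22 days.
- Late window: 387 − 22 + 1 = 366 days.
- Sum: 22 + 366 = 388 day-slots over 387 distinct days, so exactly one day, D22, is in both.
- With the late window starting at D23: 22 + 365 = 387, and no day is shared.

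**Where the shared day falls once each event has one last vaccination**
- Dose 2 on study day 22: onset D22 is study day 22 + 21 = 43.
- Dose 2 on study day 29: onset D22 is study day 29 + 21 = 50.
- Dose 1, with dose 2 delayed or not given: study day 22.
- Dose 1, with dose 2 on schedule: an event after dose 2 on study day 22 belongs to dose 2 with onset D01, so the dose 1 overlap essentially vanishes.

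**Share of follow-up, assuming onsets spread evenly over time** (an assumption; the documents give no SAE or AESI rate)
- 1/387 = 0.26% of the span counted from dose 1.
- 1/366 = 0.27% of the follow-up counted from an on-schedule dose 2.

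**The 387-day limit against planned follow-up after dose 2**
- Planned: 365 to 365 + 14 = 379 days, ending on study day 22 + 379 = 401, or 29 + 379 = 408.
- Label: 387 days after dose 2 is study day 22 + 387 = 409, or 29 + 387 = 416.
- The label therefore runs 387 − 379 = 8 days past the latest planned contact, and 387 − 365 = 22 days past the earliest.

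**Comparison inside the protocol.** Protocol 9.4.3 splits medically attended events at D42/D43 and D202/D203, with no shared day.

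**The case against.** The strongest reply is that this is a wording slip with almost no consequence, and much of that reply stands.

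- All analyses are descriptive (SAP 3.1), so no test, error rate or sample size depends on the boundary.
- The row covering the full 387 days is cumulative. Its overlap with the early and late rows is intended and is no fault.
- Rows that count participants need not add up even with clean windows, because a participant with events in both periods is rightly counted in each. Only event counts should add, and they would be off by the D22 onsets alone.
- The 387-day limit loses no dose 2 event, since planned follow-up ends by 379 days. The fault is in the label.
- A study-long analysis is largely foreseen: the safety analysis set in SAP 3.3 allows analysis after any dose, and SAP Table 2.1 states the SAE and AESI endpoints for the whole study. What 4.2.2.2.6 and 4.2.2.2.7 lack is a window expressed that way.

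One could also argue that D22 in the late window was meant as 22 days after vaccination, which would make the windows meet without overlapping. That may well be the intention, but it contradicts the numbering in SAP 4.2.2.2.4, where 22 days after vaccination is D23. The boundary therefore still needs correcting.

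**Conclusion.** The rule is wrong as written, with a small effect. An SAE or AESI with onset on D22 after its last vaccination is placed in both the early and the late window, and 387 days is a study-day figure attached to each dose. The size is one onset day per dose, roughly 0.26% to 0.27% of follow-up under even spread. The result rests on the onset formula in SAP 4.2.2.2.4 applying to SAEs and AESIs, which the SAP's structure and Protocol 10.3.1 support.

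A reader might infer more: that because the windows run 387 days after each vaccination, most late events are counted under both doses. The documents do not support this. SAP 4.2.2.2.3 gives every unsolicited event one last vaccination, SAEs are unsolicited events, and under that rule no study day falls under both doses. The window sections fail to restate the rule, but they do not override it.

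A reader might also infer that SAE or AESI rates by dose will be wrong because the late dose 1 row will be nearly empty. For two-dose participants, dose 1 does hold only the 21 to 28 days before dose 2. That follows from attributing events to the latest dose, with participants vaccinated with that dose as the denominator (SAP 3.4.3). A sparse row is not in itself an incorrect rate.

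**What to change.** In SAP 4.2.2.2.6 and 4.2.2.2.7:

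1. Keep the early window as onset D01 to D22 after each vaccination, as in 4.2.2.2.4.
2. Define the late window as onset D23 to the end of study follow-up, replacing the 387-day limit.
3. State that each event is assigned to the last vaccination received, following 4.2.2.2.3.
4. Label the overall row *throughout the study, after any vaccination*, and count each participant once.

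The cost is a few sentences in the SAP and matching edits to the table shells. No data collection, visit or sample size changes. The edit should be made before the database lock for the main analysis, so that the D22 boundary is settled before unblinding.
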